## Appendix 2: Survey Questions (Objective 2: PLHIV surveys)

### **Sociodemographic data (to be collected at each survey instance)**

- a. Age (years)
- b. Sex
- c. Highest educational level
- d. Marital status
- e. What is your maternal language (language you grew up with)
- f. Patient ID
- g. Year in which you began HIV care at this health facility

### **Measures for People Living with HIV**

#### Group-Based Medical Mistrust Scale (GBMMS) Items

Response categories: "Strongly agree", "Agree", "Disagree", and "Strongly Disagree"

1. People living with HIV like me trust doctors and health care workers.
2. People living with HIV like me should be suspicious of modern or conventional medicine.
3. People living with HIV like me should be suspicious of information from doctors and health care workers.
4. People living with HIV like me receive the same medical care from doctors and health care workers as people from other groups.
5. Doctors have the best interests of people like me in mind.
6. Doctors and health care workers sometimes hide information from people like me.
7. I have personally been treated poorly or unfairly by doctors or health care workers because of who I am.

#### Patient Satisfaction

Response categories: "Strongly agree", "Slightly agree", "Neutral", "Slightly disagree", "Strongly disagree"

1. The provider takes care of me.
2. The provider explains the reasons for any requested medical tests.
3. The provider explains things in a way that is understandable.

4. I am confident of the health care providers' knowledge and skills.
5. Medical providers show respect for what I say.
6. The provider listens to me carefully.
7. The provider cares about me as a person.
8. The provider encourages me to talk about all my health concerns.
9. The provider spends enough time with me.

*Perceived Provider Stigma (adapted from multiple sources)*

Response categories: "Strongly agree", "Agree", "Disagree", and "Strongly Disagree"

1. Do healthcare workers touch you during your examination? (Yes/No)  
If no, why do you think they avoid touching you?  
a) Because I have HIV   b) other reason (Please specify)
2. Telling a health care worker I have HIV is risky because they may disclose my status to others.
3. People with HIV are treated worse than patients without HIV by health care workers.
4. Most health care workers are uncomfortable around someone with HIV
5. Some health care workers do not care if someone with HIV lives or dies.

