**b. Inclusion/Exclusion Criteria:**

1. PLHIV (for medical file review)

Inclusion:

- Adult individuals, 18 years of age or older
- Active in care (i.e., not in default)
- Receiving HIV care and treatment at one of the four study sites.

2. PLHIV (for survey participation)

Inclusion:

- Adult individuals, 18 years of age or older
- Active in care (i.e., not in default)
- Receiving HIV care and treatment at one of the four study sites.
- Sought care at health facility on the day of survey data collection

Exclusion (for survey participation only):

- Any clinical or mental condition (for example, but not limited to: patients with delusions, hallucinations, impaired cognitive function, mental retardation, medical condition with physical deterioration, or under the influence of drugs or alcohol at the time of study recruitment), that as per the investigator's opinion/assessment, would preclude provision of informed consent or make study participation unsafe or unethical;
- Being at the health facility for reasons other than their own medical appointment and/or picking up their own medication;
- Those who do not have routine care at the selected health facility (e.g., individuals who receive HIV care and treatment at a different facility than their own due to stigma or other reasons).

3. Health Care Workers

Inclusion:

- Adult individuals, 18 years of age or older;
- working as physicians, nurses, medical technicians, health counselors, community health care workers, or other clinical and non-clinical staff (e.g.,

receptionists, data entry clerk) who provide health services to adults living with HIV at one of the four study sites;

- willing to be followed as a study participant during the 6-month study period, and does not intend to transfer to another HF during the study period (per investigator's assessment at time of recruitment), as self-reported.
- Be able to read and write in Portuguese, as self-reported.

Exclusion:

- Those who are not permanent members of the health facility staff (i.e., floating providers that work at multiple sites in a given week);
- Any clinical or mental condition, including influence of drugs or alcohol at the time of study recruitment, that as per the investigator's opinion/assessment, would preclude provision of informed consent or make study participation unsafe or unethical;

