People living with HIV (survey): The study team will recruit participants to complete the baseline and endline surveys at the time the individuals are leaving an appointment for HIV care at one of four eligible health care facilities. Recruitment will be done using convenience sampling when the individual exits the health facility after receiving care. If the individual is interested in participating in the study, a study assistant will bring them into a private room to discuss their eligibility and study procedures (complete surveys at study baseline or endline, i.e., 6 months after the study begins, and to the use of a subset of data from their medical records regarding ART medication pick-up history within the previous 6 months). If eligible and they agree to participate, their informed consent will be obtained by the study assistant at the health facility. Participants can withdraw at any time without impact on the clinical care they are receiving.

People living with HIV who are followed as part of routine care (estimated n=16,000): The study team will not formally recruit and consent these individuals to participate in the study, as only a chart review will be performed. For the inclusion of these individuals' data, we will seek a waiver of informed consent, to be developed and included in the submission to the ethics committees/Institutional Review Board (IRB), to access their retention data and viral load results over the course of the study.

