#### **Objective 2:**

With Objective 2 most of our outcomes are continuous measurements, and analyses will be similar to those described above: linear mixed effects models that take advantage of the factorial nature of outcome, with clusters defined as study sites, and unadjusted and adjusted for a small number of PLHIV-level covariates (age, sex, educational level, marital status, language, duration on ART, and history of ART medication pick-ups within the previous 6 months). For binary outcomes (e.g., undetectable viral load), we will fit generalized linear mixed effects models with a logit link function.

Every patient is given 30, 60, 90, or 180 days to pick up their ART medication, as indicated in the medical charts. If a patient picks up medication after the indicated/scheduled date, they will be considered "non-adherent" for each day after their specific pick-up date; this will be assessed over the course of the 6-month follow-up and will be treated as a continuous variable (a proportion between 0 and 1 for each participant). Participants who are lost to follow-up from the health facility during the 6-month follow-up period will be considered "non-adherent" for the days that they are lost. For persons who die or are known to have transferred care outside of the catchment area, the proportion of time on medication will be computed using only time prior to death or transfer of care. For our primary retention outcome (proportion of time on medication), normality assumptions are unlikely to hold, perhaps even after data transformation. Hence, we will fit a cumulative probability model (CPM) with fixed effects for the clinics. The CPM is well-suited for this setting because it does not require symmetry/normality in the outcome (which is bounded between 0 and 1 and likely not normal); in the absence of covariates, it reduces to the Wilcoxon rank sum test. The CPM has been shown to perform well in settings investigating medication adherence. Specifically, the distribution of the proportion of time on medication will be modeled as

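### The first perceived-stigma item has no 'not examined' answer, its follow-up presupposes avoidance, and no scoring rule covers its Yes/No format, so unexamined patients can be counted as stigmatised

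*Combined protocol and SAP*

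**What the plan says.** Appendix 2, Perceived Provider Stigma, prints one response scale for the block: "Response categories: 'Strongly agree', 'Agree', 'Disagree', and 'Strongly Disagree". Item 1 does not use it. It asks "Do healthcare workers touch you during your examination? (Yes/No"), and a No leads to "If no, why do you think they avoid touching you", with two answers: (a) that the patient has HIV, or (b) "other reason (Please specify"). Items 2-5 are agreement statements.

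Section 7.b excludes from the survey anyone "Being at the health facility for reasons other than their own medical appointment and/or picking up their own medication". A visit made only to collect one's own medication is therefore eligible. Section 7.e describes recruitment "at the time the individuals are leaving an appointment for HIV care at one of four eligible health care facilities" and adds: "Recruitment will be done using convenience sampling when the individual exits the health facility after receiving care". Section 8.a allows different patients to be recruited at baseline and endline.

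On analysis, Section 10 (Objective 2) says "With Objective 2 most of our outcomes are continuous measurements, and analyses will be similar to those described above". It provides a logit mixed model for binary outcomes and lists adjustment covariates, and visit type is not among them. The only text on how questionnaire scores are built is the mention of summed Likert questions under Objective 1. No section says how item 1 or its follow-up is scored. Neither the survey form (Appendix 2) nor the survey participants' record extract (Appendix 10) records whether the visit was a consultation or a pick-up, or whether the patient was examined.

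**The concern.** A No to item 1 can mean two different things: staff examined the patient without touching, or there was no examination. The form gives both patients the same code, and the follow-up then tells both that staff avoided them. The respondent did not say that, and HIV is the first reason offered.

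Perceived provider stigma is one of three patient-survey measures and the one aimed directly at stigma, in a trial that includes anti-stigma training. If the share of unexamined patients differs between sites or rounds, that difference can enter the comparison as a difference in stigma. Convenience sampling at exit does nothing to hold the share constant. If unexamined patients stay in the denominator, a real change in avoidance among examined patients is also diluted. Because item 1 does not fit the printed scale and has no scoring rule, its handling would be settled after the data are in.

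**Working it through.** **1. The plan's own figure.** Section 7.c gives survey detectable differences of 0.55, 0.71 and 0.96 SD at ICC 0.025, 0.05 and 0.10, with 80 surveys per facility. I compare two sites with two sites (160 against 160), two-sided alpha 0.05, 80% power:

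- Design effect = 1 + (80 - 1) x ICC = 2.975, 4.95, 8.90.
- Detectable difference = (1.96 + 0.84) x sqrt(2 x design effect / 160) = 0.540, 0.697, 0.934 SD.
- With a t distribution on the effective sample size, power at the stated differences is 80.7%, 80.2% and 79.8%.

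The stated figures reproduce. The wording problem changes none of them. They serve here only as a yardstick.

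**2. What a No would contain.** The documents give neither a rate of unexamined visits nor a rate of avoidance, so both are assumptions. Let u be the share unexamined and p the share of examined patients whom staff avoid touching. Assume every unexamined patient answers No.

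- No rate = u + (1 - u) x p
- Share of No answers from unexamined patients = u / (No rate)

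| u | No rate, p = 5% | Share unexamined | No rate, p = 10% | Share unexamined |
|---|---|---|---|---|
| 10% | 14.5% | 69% | 19% | 53% |
| 20% | 24% | 83% | 28% | 71% |
| 30% | 33.5% | 90% | 37% | 81% |
| 50% | 52.5% | 95% | 55% | 91% |

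**3. False difference if every No is scored as stigma.**

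- u = 20% against 40%, p = 10% in both groups: 28% against 46%, or 18 points. At the average of 37%, SD = sqrt(0.37 x 0.63) = 0.483, so 0.18 / 0.483 = 0.37 SD. This is below all three of the plan's thresholds.
- u = 30% against 60%, p = 0: 30 points. At the average of 45%, SD = sqrt(0.45 x 0.55) = 0.497, so 0.30 / 0.497 = 0.60 SD. This is above 0.55 SD (27 points) but below 0.71 SD (35 points) and 0.96 SD (48 points).

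**4. False difference if only answer (a) is scored.** Let r be the share of unexamined patients who accept the HIV reason, and assume that every examined patient who was avoided chooses (a). With u = 20% against 40% and p = 10%, the difference is 0.20 x r - 0.20 x 0.10:

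- r = 0: -2 points (dilution only)
- r = 10%: 0 points
- r = 25%: 3 points
- r = 50%: 8 points

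With u = 30% against 60%, p = 0 and r = 10% to 30%, it is 0.30 x r = 3 to 9 points. In that scenario, a true effect among examined patients is diluted by 30% in one group and 60% in the other if everyone stays in the denominator.

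The scoring rule, which the plan does not give, therefore decides whether the artefact is small or large.

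**The case against.** The strongest reply is that a reader might infer from the form that visit type and the leading prompt are recorded as stigma, and the documents do not say that. No section codes No as stigma. Answer (b) is open text, where a patient can say there was no examination, and a surveyor is present to help record it. Item 1 is in the general present tense and is not tied to that day, and respondents must have their routine care at the facility, so someone collecting medication can answer from earlier visits. Section 7.e describes recruitment on leaving an appointment, so pick-up-only respondents may be few. All of this stands, and it limits the problem.

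A reader might also infer that the data could never be repaired. That is too strong. The open text in (b) can be classified. Appendix 9 lists appointment dates, pick-up dates and patient ID for all patients at the sites, and the survey also takes patient ID, so linkage might recover visit type. However, Section 8.a describes only pick-up history for survey participants, and an appointment date does not show that an examination took place.

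The objection leaves three things unanswered. The eligibility rule still admits pick-up-only visits. The follow-up is leading whichever visit the patient has in mind. Answer (b) helps only if a rule says to use it. Item order matters less: the mistrust questions, one of them on poor or unfair treatment, already come before this block.

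**Conclusion.** The point holds as a defect of form and scoring. Item 1 lacks a 'not examined' answer, its follow-up presupposes avoidance, and its Yes/No format does not fit the block's scale. With no scoring rule and no record of visit type, unexamined patients can be counted as stigmatised.

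The size cannot be known from the documents. Under the assumptions shown, the false difference on item 1 alone runs from about zero to 9 points if only the HIV reason counts. It is 18 to 30 points if every No counts and the share unexamined differs by 20 to 30 points between groups. It would be tempting to say that the trial would report such an artefact as an effect. The documents do not support this: the imbalance is assumed, and even the 30-point case exceeds only the smallest of the plan's three detectable differences.

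Importance is minor. This is one item of five, in a survey that Section 7.c calls exploratory, and Section 8.b places the primary patient measures elsewhere. It is worth correcting because the correction is cheap.

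**What to change.** If the baseline patient survey has not been done:

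- Add a pre-coded answer to item 1: 'not examined / no examination needed'.
- Word the follow-up neutrally: 'If no, why not?'
- Record whether the visit was a consultation or a pick-up only.
- State in the analysis plan that item 1 is scored separately as 'not touched because of HIV' among examined patients, using the logit mixed model already planned for binary outcomes, and that the continuous stigma score is formed from items 2-5 only.

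Moving item 1 after items 2-5 is optional.

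The cost is a short questionnaire edit and a sentence or two in the analysis plan, with no extra patients or visits. The downside is comparability. Appendix 4 already cites results from the health care worker survey, and Section 15 places the patient baseline in Months 1-2, close to the health care worker baseline in Month 1. The patient baseline may therefore be complete, and a reworded item 1 could not be compared between rounds. In that case, keep the baseline wording, add the 'not examined' code and visit type at endline, classify the baseline 'other reason' text, and apply the separate scoring rule to both rounds before any comparison by arm.

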## Appendix 3: Interview Guides for Health Care Workers Who Participated in the Interventions (Objective 1)

### **Demographic information**

Age

Sex

Marital status

Education level

Academic training (*all levels achieved*)

Job position

Sector of work activity (in HF)

Community/province where born

Health care facility currently employed

Fluent in local language?

Family living with you in Zambézia (partner, children)?

Length of time you have been a health care worker?

Length of time you have been a health care worker at this health facility?

In addition to this HF, have you worked in particular in private clinics?

Are you a student in addition to working?

How many hours do you work per week (< 40 hours, 40 hours, > 40 hours a week)?

Do you have any close relatives living with HIV?

### **In-depth Interview Questions**

1. Can you tell me about your experience attending the program? [specific which one depending on their site]

2. Think back to when you first hear about the program. Why did you decide to participate? What expectations did you have for the program when you first heard about it?

3. Now think about the program after you have participated. Did the program meet your expectations? If so, tell me ways that the program met your expectations.

- a) What was good about the program? (What did you like about the program?)
- 4. Tell me ways the program did not meet your expectations? Are there any other expectations you had from the sessions that were not met?
  - a) In what ways did the program fail to succeed?
- 5. Can you tell me if the program changed the way you think or interact with colleagues or patients at work?
- 6. Can you tell me ways we could improve the program? [Probe: topic areas to cover, ways to deliver support, group vs individual setting]
- 7. Is there anything we could do to advocate for health care providers at the provincial or national level in order to improve their wellbeing?
  - a) What do you need to be successful (in general and at work)?
  - b) What do you need to improve your wellbeing?

## Appendix 4: In-depth Interview Guide for Health Care Workers at Intervention Sites – Moral Injury Questions (Objective 3)

### **In-depth interview guide about moral injury/ moral trauma intervention and suicide**

*[Interviewer will start the interview by summarizing moral injury study findings with the participant:]*

In our survey done with health care workers (HCW) in the area, we found that people had higher rates of something called “moral injury” than expected. Moral injury can occur when someone experiences, witnesses, or is involved in a situation(s) that conflicts with their own values or beliefs.

One example of an event that may lead to moral injury includes a patient who comes in for care that you know how to provide but you lack the medications or equipment to treat them – perhaps they suffer or die because you are unable to treat them, which goes against your own values/beliefs about patient care.

Another example is someone comes in at 22hrs with serious bleeding due to a pregnancy complication – and she is too ill to save with the treatment/materials that are on hand at the clinic. But instead of providing her support, you observe another HCW place the blame on the patient for “waiting to come in”, and this other HCW’s behavior goes against your own values for how to best support patients.

In our study, 36% of HCW participants showed signs of moderate moral injury. Moral injury can lead to higher levels of anxiety and depression, and potentially to suicidal ideation.

We want to chat with you about treating patients at your health facility and how the provision of care can negatively impact the health of HCW. We also want to talk with you about how we can help people working in the health system.

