## 15. Timeline

Time (month)	Activities/Description
Month 1	Recruit health care workers from four health facilities (n=100).

Month 1	Among HCW , assess baseline measures of (1) Resilience (2) Stigma (3) Burnout (4) Depersonalization (5) Moral Injury Questionnaire		
Months 1-4	Resilience/Wellness Intervention arm sessions; held bi-monthly	Resilience/Wellness and anti-stigma arm sessions, held bi-monthly	Anti-stigma arm intervention only sessions; held bi-monthly
Months 1-2 & Months 6-7	Recruit a sub-group of PLHIV patients receiving any HIV care and treatment into the study at the four study sites (total n=320) to assess impact of the interventions on medical mistrust, patient satisfaction, and perceived stigma from health care providers via baseline (study start) and end-line (approximately 6 months after study start) surveys.		
Months 1-12	Collect routine clinical data (retention, viral load) from all patients enrolled in care and treatment at the four study sites (n estimated approximately to be 16,000).		
Months 5-7	Among HCW , collect post-intervention surveys (repeat same measures as used at baseline, except for #5 Moral Injury Questionnaire) at all sites (control and intervention).		
Months 8-9	Recruit a sub-group of HCW participants at the three intervention sites for in-depth interviews related to moral injury/ moral trauma.		
Months 8-14	Conduct data analysis of survey outcomes among PLHIV and HCW.		
Months 10-11	Conduct surveys to assess depression, anxiety, and suicidality		
Months 12-15	Conduct data analysis of clinical outcomes among PLHIV.		
Months 12-18	Disseminate findings via community meetings with community members and clinicians		

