#### *Interview questions:*

- 1) After hearing what moral injury is (*remind them if necessary*), how important do you think this problem is in this health facility or in the province?
  - a. probe: In your opinion, how common do you think this experience of moral injury might be among HCW in this area?
  - b. probe: Have you ever experienced moral injury/ moral trauma? If so, please can you describe your experience?
  - c. probe: How does it impact HCW’s mental health (e.g., depression, anxiety, apathy, etc.)?
  - d. probe: How does it affect the way they deliver care? (e.g., do they seem to have less empathy for patients? Do they have greater frustration with or depersonalization of patients?)
- 2) Do you know of any HCW who have become suicidal or had thoughts of suicide? If so, can you tell me about their experiences?

3) What are the biggest issues with working in the health field and in this health system in particular that could be causing high levels of moral injury? How have these issues impacted you?

- a. probes: Lack of medication, lack of materials, lack of human resources, work atmosphere, management issues, level of support from supervisors, others?
- b. probe: Are there any other minor issues related to working in the health field that could be causing moral injury? If so, can you describe how these impact you?

4) We understand that the health system is under capacitated, but we still want to support HCW. In your opinion, what could be done to reduce either the experience of or the impact of moral injury on HCW?

- a. Some changes have to be done at the health system level- like making sure there are enough drugs or hiring more people to help deliver care. What suggestions would you have to improve the health care system?
  - i. Do you think this would be feasible to implement?
- b. Some services could be provided to individual HCW who are struggling- like offering counseling or support services to them specifically.
  - i. How can we help HCW who feel lots of anxiety or depression?
  - ii. How can we help HCW who feel like the health system is failing patients?
  - iii. How can we help HCW who have thoughts of suicide or become suicidal?
    - 1. Do you think any of these would be acceptable to HCW? Would they be feasible to implement?

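### Appendix 4 reads out the study's own moral-injury result before asking interviewees how important and how common the problem is, so those answers are led

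*Combined protocol and SAP*

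**What the plan says.** Study Question 5 (Section 6) has two parts: whether health care workers (HCW) experience or are at risk of moral injury, and which services might help them. Section 8a, under the qualitative interviews on moral injury, plans 20 to 40 interviews with HCW from the intervention sites. Their aims include views on whether moral injury is present locally, how it affects work and wellness, and what support would be useful. Section 10, Objective 3, plans thematic coding that covers its experience and occurrence.

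The guide in Appendix 4 fixes the order: "Interviewer will start the interview by summarizing moral injury study findings with the participant". The opening says "we found that people had higher rates of something called" moral injury than had been expected. It defines the term, gives two clinical examples, and reports that "36% of HCW participants showed signs of moderate moral injury". It adds: "Moral injury can lead to higher levels of anxiety and depression, and potentially to suicidal ideation".

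The questions follow. Question 1 asks how important the problem is in the facility or province. Probe 1a reads "In your opinion, how common do you think this experience of moral injury might be among HCW in this area". Probe 1b asks about the interviewee's own experience, 1c about effects on mental health, and 1d about effects on the care delivered. Question 3 asks about features of the work "that could be causing high levels of moral injury".

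**The concern.** An interviewee who has just heard a percentage, a remark that it is high and a list of its consequences is then asked for a view on those same three matters. Agreement may reflect personal observation or simply the interviewer's opening, and the transcript cannot separate the two. Presence and occurrence are stated aims of these interviews, so question 1 is not a mere warm-up. If its themes are later reported as supporting the survey result, the study will partly be hearing its own figure repeated.

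**Working it through.** No sample-size, power or error-rate figure is involved. The 36% is given without numerator, denominator or cut-off, so it cannot be recomputed. The check is of order and content.

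**Step 1. Set the preamble beside question 1 (both in Appendix 4).**

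| Told before any question | Asked afterwards |
|---|---|
| Rates were above expectation | Question 1: how important is the problem? |
| 36% showed moderate signs | Probe 1a: how common is it? |
| It can lead to anxiety, depression and possibly suicidal ideation | Probe 1c: how does it affect mental health? |

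Question 1 has a stem and four probes, five prompts in all. Three of the five (stem, 1a, 1c) follow a direct statement on the same matter. Probes 1b and 1d do not.

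**Step 2. Does question 1 need the findings?** Its stem refers back only to the explanation of what moral injury is. The definition and examples are enough; the percentage and its consequences are not needed.

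**Step 3. Are the interviewees separate from the source of the figure?** Section 7e draws them from HCW already enrolled. Section 8a asks all enrolled HCW to complete the survey, and the moral-injury scale is in its baseline round. If the 36% comes from that round, as the wording of Appendix 4 suggests, many interviewees probably contributed to it. Reading the figure back and then asking how common the problem is cannot corroborate it.

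**Step 4. What is not touched?** Table 4 and Appendix 1 give the moral-injury scale at baseline only, and the Timeline puts it in Month 1. The Timeline puts recruitment for the interviews in Months 8-9. The preamble cannot alter a score recorded months earlier.

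**Step 5. Compare with the guide's own practice.** The burnout result (1% with moderate levels) is held back to question 5, where interviewees are asked to explain it. No one is asked how common burnout is after hearing the figure. The same arrangement would serve for moral injury.

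**The case against.** The best defence is that feeding results back is deliberate. The guide presents survey findings and asks staff to account for them and suggest remedies; question 3 on causes and question 4 on support work well that way. The interviews gather views, the coding is thematic, no prevalence is estimated from them, and the plan nowhere calls probe 1a independent evidence. All of this stands, and it limits the harm to question 1. It does not justify the order, because the same feedback can be given after question 1 with nothing lost.

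A reader might go further and infer that the depression, anxiety and suicidality survey (Question 6) is biased, since only intervention-site staff hear the preamble and the Timeline places that survey in Months 10-11, after the interviews. With at most 25 HCW per site, the exposed share would be 20/75 = 27% to 40/75 = 53% at the three intervention sites, against 0 of 25 at the control site. The documents do not carry this to a finding of bias:

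- Section 10, Objective 3, expects no intervention effect on these measures and plans descriptive summaries only. The look by gender, age and site is for trends, without a test.
- Each arm is one site, so a site difference is already inseparable from the facility and from the training. The resilience sessions themselves teach staff to recognise burnout and when to seek care.
- The gap is unsettled. The Timeline gives 10 - 9 = 1 to 11 - 8 = 3 months. Sections 5, 7e and 10 count 10-11 months from the intervention; if that means from the last sessions in Month 4, the survey falls in Months 14-15 and the gap is 14 - 9 = 5 to 15 - 8 = 7 months. Section 8a counts from enrollment, and the Table 4 header implies an earlier survey.
- No size or direction of a priming effect is given. For scale only, an assumed shift of 5 to 20 percentage points among interviewees would move the intervention-control contrast by 5 × 0.267 = 1.3 to 20 × 0.533 = 10.7 points. At an assumed prevalence of 20%, the simple 95% half-width for 75 against 25 is 1.96 × √(0.2 × 0.8 × (1/75 + 1/25)) = 18 points, ignoring clustering.
- Showing survey results with and without interviewees would not settle it, because interviewees are chosen purposively and the comparison would mix selection with priming.

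**Conclusion.** The point holds for the interview answers on perceived importance, frequency and consequences. They are led by the study's own result for every interviewee, and they cannot independently inform the presence part of Question 5. The baseline scale score is unaffected, and the anchor on frequency does not reach the part of Question 5 about services.

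For Question 6, no more can be said than that only intervention-site staff are interviewed and that the Timeline puts those interviews before a descriptive survey.

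The conclusion rests on the guide being delivered in its printed order. How far answers shift is not known from the documents. The matter is minor: no estimate, test or trial outcome depends on it.

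**What to change.** In Appendix 4, split the opening. Read the definition and the two examples first, without the statement that rates were above expectation. Ask question 1 with probes 1a to 1d. Then read the findings (above expectation, 36%, the link to anxiety, depression and suicidal ideation) and go on to the later questions, where the feedback is useful.

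Probe 1c itself names depression and anxiety as examples, so moving the preamble will not remove every cue from that prompt.

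The cost is a small reordering of the guide, with no extra data collection and no change to sample size. If interviews have already been done in the present order, note the guide order for each transcript and take it into account when the themes from question 1 are written up.
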